3.6 Post Study Drug Study Follow up

In this study, PFS is a key endpoint of the study. Post study follow-up is of critical importance and is essential to preserving subject safety and the integrity of the study. Subjects who discontinue study drug must continue to be followed for collection of PFS. Subjects who discontinue study therapy must also continue to be followed for overall survival data in line with Section 5 until death or the conclusion of the study.

3.6.1 Withdrawal of Consent

Subjects who request to discontinue study drug will remain in the study and must continue to be followed for protocol specified follow-up procedures. The only exception to this is when a subject specifically withdraws consent for any further contact with him/her or persons previously authorized by subject to provide this information. Subjects should notify the investigator of the decision to withdraw consent from future follow-up **in writing**, whenever possible. The withdrawal of consent should be explained in detail in the medical records by the investigator, as to whether the withdrawal is from further treatment with study drug only or also from study procedures and/or post treatment study follow-up, and entered on the appropriate CRF/eCRF page. In the event that vital status (whether the subject is alive or dead) is being measured, publicly available information should be used to determine vital status only as appropriately directed in accordance with local law.

3.6.2 Lost to Follow-Up

All reasonable efforts must be made to locate subjects to determine and report their ongoing status. This includes follow-up with persons authorized by the subject as noted above. Lost to follow-up is defined by the inability to reach the subject after a minimum of three documented phone calls, faxes, or emails as well as lack of response by subject to one registered mail letter. All attempts should be documented in the subject's medical records. If it is determined that the subject has died, the site will use permissible local methods to obtain the date and cause of death.

If investigator's use of third-party representative to assist in the follow-up portion of the study has been included in the subject's informed consent, then the investigator may use a Sponsor-retained

third-party representative to assist site staff with obtaining subject's contact information or other public vital status data necessary to complete the follow-up portion of the study. The site staff and representative will consult publicly available sources, such as public health registries and databases, in order to obtain updated contact information. If after all attempts, the subject remains lost to follow-up, then the last known alive date as determined by the investigator should be reported and documented in the subject's medical records.

4. STUDY DRUG

Study drug includes both Investigational [Medicinal] Product (IP/IMP) and Non-investigational [Medicinal] Product (Non-IP/Non-IMP) and are listed in Table 4.-1.

Product Description / Class and Dosage Form	Potency	IMP/Non-IMP	Blinded or Open Label	Packaging / Appearance	Storage Conditions (per label)
Elotuzumab Powder for Solution for Infusion	300 mg/vial or 400 mg/vial	IMP	Open Label	Vial	Refer to the label on the container and/or the pharmacy manual.
Nivolumab Solution for Injection	100 mg (10 mg/mL)	IMP	Open label	Vial	Refer to the label on the container and/or the pharmacy manual.
Dexamethasone Tablets	2 mg and 4 mg and various strengths	Non-IMP	Open-label	Various packing configurations	Refer to label on container or package insert / summary of product characteristics
Dexamethasone Solution	4 mg/mL, 8 mg/mL and various strengths	Non-IMP	Open-label	Various packing configurations	Refer to label on container or package insert / summary of product characteristics
Pomalidomide Capsules	1 mg, 2 mg, 3 mg and 4 mg	IMP	Open label	Various packing configurations	Refer to label on container or package insert

Table 4.-1:Study Drugs for CA204142

Pomalidomide (Pomalyst®), Dexamethasone tablets and solution for IV infusion will be obtained by the investigating site's standard prescribing procedures.

4.1 Investigational Product

An investigational product, also known as investigational medicinal product in some regions, is defined a pharmaceutical form of an active substance or placebo being tested or used as a reference in a clinical study, including products already with a marketing authorization but used or assembled (formulated or packaged) differently than the authorized form, or used for an unauthorized indication, or when used to gain further information about the authorized form.

The investigational product should be stored in a secure area according to local regulations. It is the responsibility of the investigator to ensure that investigational product is only dispensed to study subjects. The investigational product must be dispensed only from official study sites by authorized personnel according to local regulations.

4.2 Non-investigational Product

Other medications used as support or escape medication for preventative, diagnostic, or therapeutic reasons, as components of the standard of care for a given diagnosis, may be considered as non-investigational products.

In this protocol, non-investigational product(s) are: dexamethasone tablets and concentrate for solution for IV infusion, or products used for Elotuzumab premedication Section 4.5.3.1 or thromboprophylaxis (Section 3.4.1).

4.3 Storage and Dispensing

The product storage manager should ensure that the study drug is stored in accordance with the environmental conditions (temperature, light, and humidity) as determined by BMS. If concerns regarding the quality or appearance of the study drug arise, the study drug should not be dispensed and contact BMS immediately.

Study drug not supplied by BMS will be stored in accordance with the package insert.

Investigational product documentation (whether supplied by BMS or not) must be maintained that includes all processes required to ensure drug is accurately administered. This includes documentation of drug storage, administration and, as applicable, storage temperatures, reconstitution, and use of required processes (eg, required diluents, administration sets).

Procedures for proper handling and disposal of anticancer drugs should be considered.

The investigator or designee accepts responsibility for documenting traceability and study drug integrity in accordance with requirements applicable under law and the standard operating procedures (SOPs)/standards of the sourcing pharmacy. These records should include:

- label identification number or batch number
- the amount dispensed to and returned by each subject, including unique subject identifiers dates and initials of person responsible for Investigational Product dispensing/accountability, as per the Delegation of Authority Form.

4.3.1 Elotuzumab

The lyophilized elotuzumab drug product should be stored at 2° to 8°C. Before administration the drug product must be reconstituted with Sterile Water for Injection, USP, and then further diluted in 0.9% sodium chloride normal saline, United States Pharmacopoeia (USP), as per the instructions in Appendix 3. The dose of elotuzumab to be administered to a subject will be calculated by multiplying the subject's weight (kg) by 10 or 20 mg/kg. The subject's predose weight on Day 1 of each cycle will be used to calculate the dose for each cycle. The screening weight can be used for the Cycle 1 dose calculation. Each dose should be infused as per instructions in Appendix 3. The infusion start and stop time will be recorded in the CRF/eCRF. If the infusion is stopped mid-session for any reason, the stop/start time must be recorded together with an explanation. Please refer to the pharmacy manual for detailed guidance on storage, preparation and administration.

4.3.2 Nivolumab

Nivolumab will be administered at a dose of 240 mg as an intravenous infusion over 30 minutes every 2 weeks (Days 1 and 15 of each 28 day cycle) during Cycles 1 through 4. Starting Cycle 5 and beyond, nivolumab will be administered at a dose of 480 mg as an intravenous infusion over 30 minutes every 4 weeks (Day 1 of each 28 day cycle).

Please refer to the nivolumab investigator brochure and/or pharmacy reference sheet for guidelines on drug preparation and administration. Flush the intravenous line at the end of infusion.

Nivolumab vials must be stored at a temperature of 2°to 8°C and should be protected from light and freezing. Recommended safety measures for preparation and handling of nivolumab include laboratory coats and gloves.

4.3.3 Pomalidomide

Pomalidomide is an analogue of thalidomide. Thalidomide is a known human teratogen that causes severe life-threatening human birth defects. If pomalidomide is taken during pregnancy, it may cause birth defects or death to an unborn baby.

Because of this potential toxicity and to avoid fetal exposure to pomalidomide, pomalidomide is only available under a special restricted distribution program. This program is called Pomalyst[®] REMS. Pomalidomide must only be dispensed to subjects who meet all the conditions of Pomalyst[®] REMS. Subjects who have the potential of pregnancy in Pomalyst[®] REMS must be instructed about contraception and undergo the scheduled pregnancy tests.

Please see the US package insert for additional information for prescribing to female subjects and male subjects about this restricted distribution program.

Subjects should not break, chew or open the capsules. Pomalidomide should be taken without food (at least 2 hours before or 2 hours after a meal). Only enough pomalidomide for one cycle of therapy will be supplied to the patient each cycle in accordance with Pomalyst[®] REMS.

4.3.4 Dexamethasone

Dexamethasone tablets and solution for IV infusion is considered NIMP for this study and will not be provided by the sponsor. It will be obtained by the investigating sites standard prescribing procedures. Marketed product will be utilized for this study and should be stored in accordance with the package insert.

4.4 Method of Assigning Subject Identification

After the subject's eligibility is established and informed consent has been obtained, the subject must be enrolled into the study by calling an interactive voice response system (IVRS) to obtain the subject number. The following information is required for subject enrollment:

- Date of Birth
- Gender
- Site number
- Date that informed consent was obtained

Instructions on the use of IVRS will be provided in a separate document.

4.5 Selection and Timing of Dose for Each Subject

Table 4.5-1: Treatment Schedule for EPd Cohort and Cross over Patients from EN Cohort

Cycle	Cycle 1				Cycle 2			Cycle 3 and beyond ^b				
Day	1	8	15	22	1	8	15	22	1	8	15	22
Elotuzumab	10 mg/kg	20 mg/kg										
Dexamethasone ^a	Ļ	Ļ	Ļ	Ļ	Ļ	Ļ	Ļ	Ļ	Ļ	Ļ	Ļ	Ļ
Pomalidomide	Days 1-21				Days 1-21			Days 1-21				
^a See Table 4.5.2-1 for the dose of dexamethasone.												
^b Patients who cross over from the EN cohort will follow the treatment schedule for Cycle 3 and beyond												

Table 4.5-2:Treatment Schedule for the EN Cohort

Cycle	Cycles 1 and 2			Cycles 3 and 4			Cycle 5 and beyond					
Day	1	8	15	22	1	8	15	22	1	8	15	22
Elotuzumab	10 mg/kg	10 mg/kg	10 mg/kg	10 mg/kg	20 mg/kg				20 mg/kg			
Nivolumab	240 mg		240 mg		240 mg		240 mg		480 mg			

See Table 4.5.2-2 for dexamethasone IV dose administered as pre-medication for elotuzumab

4.5.1 *Pomalidomide*

Pomalidomide 4 mg will be administered orally once daily for the first 3 weeks of a 4-week cycle. Pomalidomide should be taken without food (at least 2 hours before or 2 hours after a meal). Subjects should not break, chew or open the capsules.

On the days of elotuzumab administration, the dose of pomalidomide is to be administered at least 2 hours after completion of elotuzumab dosing.

Pomalidomide delay should be performed as clinically indicated at the discretion of the investigator.

Subjects should be instructed that if a dose of pomalidomide has been missed and it has been less than 12 hours since the subject's regular dosing time, to take pomalidomide as soon as the subject remembers. If it has been more than 12 hours, the dose must be skipped. Subjects should not take 2 doses at the same time

Females of reproductive potential must have negative pregnancy testing and use contraception methods before initiating pomalidomide.

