4.5.8 Dose Delay, Interruption, or Discontinuation for All Subjects

Please refer to Sections 4.5.8.1, 4.5.8.2, 4.5.8.3, and 4.5.8.4 for drug-specific delay guidance.

For each cohort, if the dose of one drug in the regimen (ie, pomalidomide, dexamethasone, nivolumab, or elotuzumab) is delayed, interrupted, or discontinued, the treatment with the other drugs may continue as scheduled. However, in the EPd cohort, if dexamethasone is delayed or discontinued discuss ongoing elotuzumab administration with the Medical Monitor. Subjects experiencing a 56 day delay in all study drugs due to an adverse event(s) related to study treatment must be discontinued from study drug. Subjects experiencing delays unrelated to study therapy, for example due to radiation therapy, may delay study treatment after discussion with the medical monitor.

Each cycle is 28 days. While dose delays or interruptions are permitted, the start of each cycle cannot be delayed and is fixed (ie, anchored) relative to Cycle 1 Day 1. Adjustments to the Cycle 1 Day 1 anchored schedule should not be performed. Missed doses should be skipped, not delayed, if not given within the allowed window.

Subjects may continue on study therapy even if components of the study therapy must be discontinued. For example, a subject may continue on study therapy if elotuzumab must be discontinued for an adverse event or other reason. Patients are considered still on study therapy even if they continue solely on pomalidomide, dexamethasone, or nivolumab.

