5. STUDY ASSESSMENTS AND PROCEDURES

5.1 Flow Chart/Time and Events Schedule

Table 5.1-1:Screening Procedural Outline (CA204142)								
Procedure	Screening Visit	Notes						
Eligibility Assessments								
Informed Consent	Х	Prior to any screening procedures						
Inclusion/Exclusion Criteria	Х	Within 14 days prior to first dose of study drug						
Medical History/Treatment History	Х							
Safety Assessments								
Physical Examination	Х	Includes height and weight within 14 days prior to first dose of study drug						
Vital Signs	Х	Temperature, BP, HR, within 14 days prior to first dose of study drug						
Performance Status (ECOG)	Х	Within 14 days prior to first dose of study drug						
Serious Adverse Events Assessment	Х	Collected from the time of informed consent						
Concomitant Medications	Х	Within 14 days prior to first dose of study drug						
ECG	Х	Within 28 days of randomization						
Laboratory Assessments	•	•						
CBC, differential, platelets	Х	Within 14 days prior to first dose of study drug						
Chemistry	Х	Within 14 days prior to first dose of study drug (See Section 5.3.4)						
Serum β2-microglobulin	Х	Within 28 days prior to first dose of study drug (Central Lab Analysis)						
Albumin	Х	Within 28 days prior to first dose of study drug						
Pregnancy Test	Х	For WOCBP only, 2 pregnancy tests, one 10 - 14 days prior to start of study drug and one within 24 hours prior to start of study drug. Urine tests must have a sensitivity of at least 25 IU/L.						
Thyroid Function Tests (TFTs) (reflex to free T3/total T3, free T4 for abnormal TSH result).	X	Within 28 days prior to first dose of study drug. Required only after Amendment 02.						

Table 5.1-1:Screening Procedural Outline (CA204142)								
Procedure	Screening Visit	Notes						
Hepatitis B surface antigen (HBsAg), and hepatitis C antibody (HCV Ab) or HCV ribonucleic acid (RNA).	Х	Within 28 days prior to first dose of study drug. Required only after Amendment 02.						

Table 5.1-2:CA204142 Cycles 1 and 2 - EPd Cohort Only

Procedure	Day 1	Day 8	Day 15	Day 22	Rest Days 23 – 28	Notes			
Safety Assessments									
Targeted Physical Examination	Х					Perform prior to dosing, include weight			
Vital Signs	Х	X	Х	Х		Cycle 1: Measure vital signs pre-elotuzumab infusion, 30 minutes after the start of elotuzumab infusion, at the end of infusion, and 30 minutes after the completion of infusion Cycle 2 and beyond: evaluate prior to dosing			

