Performance Status (ECOG)	Х					Evaluate prior to dosing			
Serious Adverse Event Assessment	Х	Х	Х	Х		Evaluate prior to dosing			
Adverse Events Assessment	Х	Х	Х	Х		Evaluate prior to dosing			
Concomitant Medications	Х	Х	Х	Х		Evaluate prior to dosing			
Laboratory Tests	•			•					
CBC, differential, platelets	Х	X	Х	X		Can be drawn up to 3 days prior to study visit (See Section 5.3.4). Screening results are sufficient for Cycle 1			
Chemistry	Х					Can be drawn up to 3 days prior to study visit			
Pregnancy Test	Х	X			For WOCBP only. Urine tests must have a sensitivity of at least 25 IU/L. Test within 24 hours of Dose 1 study medication.				
Efficacy Assessments									
Myeloma Urine and Serum Lab tests	(Central Lab Analysis) Every 4 weeks from date of first dose of study drug until disease progression			b Analys s from d drug un ession	sis) ate of til disease	 Day 1 of each cycle (except Cycle 1 - refer to Screening visit for defined window as listed on Table 5.1-1) (See also: Section 5.4.2) 24-hour urine sample can be collected within ± 7 days of visit, and must be obtained in all subjects who have measurable UPEP M protein (≥ 200 mg/24 hours) at baseline with each cycle. 			
				See Section 5.4.2 for subjects without measurable urine M protein at baseline and no FLC detected by the serum test.					

Table 5.1-2:CA204142 Cycles 1 and 2 - EPd Cohort Only

Procedure	Day 1	Day 8	Day 15	Day 22	Rest Days 23 – 28	Notes
Bone Marrow Aspiration/Biopsy	For confirmation of CR if applicable or, if clinically indicated at time of suspected disease progression		plicable or, of suspected n	Bone marrow aspirate is mandatory. Bone marrow biopsy is optional. Bone marrow will be analyzed in local laboratory, with performance of IHC and/or flow cytometry to assess for sCR.		
Skeletal Imaging		If c	linically	indicat	ed	
CT/MRI assessment	As clinically indicated					
Response per IMWG uniform criteria	Every 4 weeks from date of first dose of study drug on Cycle 1 Day 1 until progression. (Cycles cannot be delayed. In the event that the first dose within a cycle is delayed or omitted, the tumor assessment should still be done on Day 1 of the cycle and should not be delayed until dosing.).					Subjects who discontinue from study treatment for reasons other than progression will continue to have tumor assessment every 4 weeks from C1D1 until progression.

Table 5.1-3:CA204142 Cycles 3 and Beyond - EPd Cohort and Cross-over Patients from EN Cohort

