Procedure	Day 1	Day 8	Day 15	Day 22	Rest Days 23 - 28	End of Treatment	Days 30 & 60 post end of treatment*	Notes
Safety Assessments				•			·	
Targeted Physical Examination	Х							Perform prior to dosing, includes weight
Vital Signs	Х					Х		Evaluate prior to dosing.
Performance Status (ECOG)	Х					Х		Evaluate prior to dosing
Serious Adverse Event Assessment	Х					Х	Х	Evaluate prior to dosing SAEs will be collected for EPd subjects up to 100 days of last dose (per Section 6.1.1).
Adverse Events Assessment	Х					Х	Х	Evaluate prior to dosing
Concomitant Medications	Х					Х	Х	Evaluate prior to dosing
Laboratory Tests				.			•	
CBC, differential, platelets	Х					Х		Can be drawn up to 3 days prior to visit. Additional samples as clinically indicated.
Chemistry	Х					Х		Can be drawn up to 3 days prior to visit (See Section 5.3.4)
Pregnancy Test	Х					X	X	For WOCBP only. Tests must occur within 24 hours prior to dosing. The pregnancy test should occur on Days 1 of each cycle. Urine tests must have a sensitivity of at least 25 IU/L. Pregnancy test must also be performed at end of treatment and at 30, 60 and 90 days off treatment. The test at 90 days off treatment may be performed locally if the patient is not scheduled to return to the center for other reasons.

Table 5.1-3:	CA204142 Cycles 3 and Beyond - EPd Cohort and Cross-over Patients from EN Cohort
--------------	--

Procedure	Day 1	Day 8	Day 15	Day 22	Rest Days 23 - 28	End of Treatment	Days 30 & 60		
							post end of treatment*	Notes	
Efficacy Assessments									
Myeloma Urine and Serum Lab tests				(Ce Every	ntral Lab An 4 weeks fror	alysis) n date of		Day 1 of each cycle (except Cycle 1 - refer to Screening visit for defined window).	
		fir	st dose	of stud	ly drug until o	disease progres	sion	24-hour urine sample can be collected within ± 7 days visit and must be obtained in all subjects who have measurable UPEP M protein (≥ 200 mg/24 hours) a baseline with each cycle.	
								See Section 5.4.2 for subjects without measurable urine M protein at baseline and no FLC detected by the serum test.	
Bone Marrow Aspiration/Biopsy	For co	onfirma	tion of of	CR if a f suspe	applicable or, cted disease j	if clinically in orogression	dicated at time	Bone marrow aspirate is mandatory. Bone marrow biopsy is optional.	
								Bone marrow will be analyzed in local laboratory, with performance of IHC and/or flow cytometry to assess for sCR.	

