Medically supervised pregnancy tests with a minimum sensitivity of 25 mIU/mL must be performed for females of childbearing potential, including females of childbearing potential who commit to complete abstinence, as outlined below.

Before starting study drug

Female Patients:

FCBP must have two negative pregnancy tests (sensitivity of at least 25 mIU/mL) prior to starting study drug. The first pregnancy test must be performed within 10-14 days prior to the start of study drug and the second pregnancy test must be performed within 24 hours prior to the start of study drug. The patient may not receive study drug until the study doctor has verified that the results of these pregnancy tests are negative.

Male Patients:

Must practice complete abstinence or agree to use a condom during sexual contact with a pregnant female or a female of childbearing potential while participating in the study, during dose interruptions and for at least 28 days following study drug discontinuation, even if he has undergone a successful vasectomy.

During study participation and for 28 days following study drug discontinuation

Female Patients:

- → FCBP with regular or no menstrual cycles must agree to have pregnancy tests weekly for the first 28 days of study participation and then every 28 days while on study, at study discontinuation, and at day 28 following study drug discontinuation. If menstrual cycles are irregular, the pregnancy testing must occur weekly for the first 28 days and then every 14 days while on study, at study discontinuation, and at days 14 and 28 following study drug discontinuation.
- → At each visit, the Investigator must confirm with the FCBP that she is continuing to use two reliable methods of birth control.
- → Counselling about pregnancy precautions and the potential risks of fetal exposure must be conducted at a minimum of every 28 days.
- → If pregnancy or a positive pregnancy test does occur in a study patient, study drug must be immediately discontinued.

- → Pregnancy testing and counselling must be performed if a patient misses her period or if her pregnancy test or her menstrual bleeding is abnormal. Study drug treatment must be discontinued during this evaluation.
- → Females must agree to abstain from breastfeeding during study participation and for at least 28 days after study drug discontinuation.

Male Patients:

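### For clinical-supply pomalidomide, Table 5.1-3 schedules half the pregnancy tests that Appendix 6 requires when menses are irregular, and no table places Appendix 6's pre-start and early tests around a first dose at EN crossover

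*Protocol*

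**What the plan says.** Section 4.5.1 makes testing a condition of starting the drug, without giving a frequency: "Females of reproductive potential must have negative pregnancy testing and use contraception methods before initiating pomalidomide".

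Appendix 6 gives the frequency. Before the start, "FCBP must have two negative pregnancy tests (sensitivity of at least 25 mIU/mL) prior to starting study drug"; the timing of the earlier one is also fixed: "The first pregnancy test must be performed within 10-14 days prior to the start of study drug". The later one falls in the last 24 hours. On treatment, tests are weekly for the first 28 days, counted from study participation, for all women of childbearing potential. Women with regular or absent menses are then tested every 28 days. For the others, "If menstrual cycles are irregular, the pregnancy testing must occur weekly for the first 28 days and then every 14 days while on study". After stopping, Appendix 6 asks for a test at day 28, or at days 14 and 28 when menses are irregular. The counselling form in the same appendix repeats this schedule.

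Table 5.1-3 governs EPd subjects from Cycle 3 and EN patients who cross over. Its note says "The pregnancy test should occur on Days 1 of each cycle", with further tests at end of treatment and at 30, 60 and 90 days. It does not mention irregular menses, Appendix 6 or REMS.

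The opening of Appendix 6 limits its scope to clinical-supply pomalidomide, although the sentence calls itself Appendix 5. It sends commercial-supply subjects to the Pomalyst REMS programme.

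**The concern.** The visit tables are what a site works from day to day, and here they are thinner than the appendix that sets the rule. A site that follows Table 5.1-3 for a woman covered by Appendix 6 would miss tests that the appendix makes mandatory. A site that follows Appendix 6 would do tests that no table provides for.

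The crossover case matters most looking forward. Revised Protocol 03 closes the EPd cohort to enrolment, so new pomalidomide starts now come mainly from EN patients who cross over. Footnote b of Table 4.5-1 puts them directly on the Cycle 3 schedule, and the crossover criteria in section 3.3.4 contain no pregnancy-test condition. What is at stake is a safety rule for a drug that section 4.3.3 says may cause birth defects or fetal death. No endpoint, sample size or analysis is affected.

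**Working it through.** The plan states no count of its own, so the check sets the schedules side by side.

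**Inputs.** Cycle length, section 4.5.8: "Each cycle is 28 days". Table 5.1-3: Day 1 only. Appendix 6: intervals of 7, 14 or 28 days, as above.

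**1. On treatment from Cycle 3** (tests per cycle = 28 / interval in days)

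| Menses | Table 5.1-3 | Appendix 6 | Ratio |
|---|---|---|---|
| Irregular | 28/28 = 1 | 28/14 = 2 | 1/2 |
| Regular or absent | 28/28 = 1 | 28/28 = 1 | 1 |

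Over 12 such cycles with irregular menses, the table gives 12 × 1 = 12 tests and Appendix 6 gives 12 × 2 = 24. The longest scheduled gap is 28 days against 14. For regular or absent menses the two agree.

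**2. After treatment.** The table's day-30 test is close to Appendix 6's day 28, and its 60- and 90-day tests go beyond the appendix. Only the day-14 test for irregular menses has no counterpart.

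**3. Before the first dose**
- *Direct EPd start.* Table 5.1-1 asks for "2 pregnancy tests, one 10 - 14 days prior to start of study drug and one within 24 hours". This matches Appendix 6, so there is no conflict.
- *Start at crossover.* The Table 5.1-1 tests precede the first EN dose, not the first pomalidomide dose. Section 3.1 has crossover begin on Day 1 of a later cycle. The EN tables (5.1-4 to 5.1-6) test on Day 1 of each cycle, so the last regular scheduled test is 28 days before crossover, outside the 10-to-14-day window. The end-of-treatment test in Table 5.1-6 is not tied to a crossover date. Table 5.1-3 does place a test in the 24 hours before the Day 1 dose. One of the two pre-start tests is therefore scheduled.

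**4. First 28 days on pomalidomide after crossover.** Weekly testing gives 28/7 = 4 tests; Table 5.1-3 gives 1. This comparison assumes that the weekly period restarts with pomalidomide. Read literally, Appendix 6 counts from study participation, and that period has already passed during EN treatment. Either way, no weekly tests are scheduled around her first pomalidomide dose.

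**5. Cycles 1 and 2 (Table 5.1-2).** The note names only the first-dose test ("Urine tests must have a sensitivity of at least 25 IU/L. Test within 24 hours of Dose 1 study medication"). The pregnancy-test row is broken in the available text: a second mark appears, but its day and span cannot be read. No count is drawn from it.

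**The case against.** The strongest objection is scope. Below Table 4.-1, the protocol says that Pomalyst is obtained through each site's usual prescribing. Section 4.3.3 says the drug is available only under REMS, and section 1.5 says subjects may follow Appendix 6 where applicable. Many, perhaps all, subjects may therefore be on commercial supply. This stands: a reader might infer that EPd subjects in general are tested too rarely, but the documents give neither the REMS frequency nor the supply split. It does not remove the defect. Inclusion criterion 3(g) accepts either programme, the scope sentence names the wrong appendix, and the tables name neither programme.

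A second objection is that safeguards exist elsewhere. Criterion 3(g) makes compliance an entry condition, and Appendix 6 requires a counselling form before each dispensing that verifies negative results. This lowers the risk that a site relies on the table alone. However, the form's explicit bar on dispensing covers the case where no tests were done, and it schedules no visit.

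Three further inferences are tempting but unsupported:
- That section 4.5.1 is itself contradicted. It concerns testing before the start, where the documents agree for direct EPd starts.
- That the tables give one test per cycle throughout. The Table 5.1-2 row cannot be read.
- That the 30-, 60- and 90-day tests conflict with Appendix 6. They mostly add to it.

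Finally, a 28-day gap is one that Appendix 6 itself accepts after the first 28 days for women with regular or absent menses. The point is inconsistency between passages, not that such a gap is wrong in itself.

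**Conclusion.** The conflict is real but limited to women of childbearing potential covered by Appendix 6. With irregular menses, Table 5.1-3 schedules half the required on-treatment tests (1 against 2 per cycle) and omits the day-14 test after treatment. For a first pomalidomide dose at EN crossover, whatever the menstrual pattern, 1 of the 2 pre-start tests is scheduled and none of the additional early weekly tests.

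The crossover result assumes that study drug in Appendix 6 means pomalidomide. The appendix's subject and the wording of section 4.5.1 support that reading, but the text does not say so outright. The number of women affected is not given and is probably small. If no subject receives clinical supply, the numerical shortfall disappears, and what remains is that the protocol does not say so or point its tables to REMS.

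**What to change.** - Reconcile the pregnancy-test rows and notes of Tables 5.1-3 and 5.3.4-1 with Appendix 6, including irregular menses and the post-treatment tests. Check the Table 5.1-2 row against the original document.
- Correct the scope sentence at the start of Appendix 6, which names Appendix 5. State in the tables which programme, Appendix 6 or REMS, governs which subjects.
- In section 3.3.4 and Table 5.1-3, make explicit the pre-start and early on-treatment testing rule that applies when pomalidomide is first given at crossover, and say from which date the early period is counted.

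Which schedule applies is for the sponsor to decide. The cost is wording in the tables, one section and one appendix, plus a few urine tests if the more frequent schedule is kept.
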